I, the Principal Investigator; by signing this protocol declare that I will permit trial-related monitoring, audits, independent Ethics Committee review, and regulatory inspections, providing direct access to source data/documents during and after the course of the trial.

I, the Principal Investigator; by signing this protocol declare that I will make the protocol and all relevant related information available to all physicians, nurses, laboratory staff and other personnel who participate in conducting this study. I will also ensure that the study team at my site receive adequate training so that they are fully informed and qualified for the conduct of the study.

I also acknowledge the paragraph relevant to study confidentiality.

PRINCIPAL INVESTIGATOR:

Title, Name:

Site:

Date:

Signed:

SCHEMA

Title: Preventing tuberculosis-associated immune reconstitution inflammatory syndrome in high-risk patients: a randomised placebo-controlled trial of prednisone

Short title: Prednisone with early ART in HIV-TB (Pred-ART trial)

Phase: III

Objective: To determine whether the addition of prednisone to the first 4 weeks of antiretroviral therapy (ART) reduces the risk of paradoxical TB-IRIS in HIV-infected patients being treated for TB who are at high risk of developing TB-IRIS (CD4 <100 cells/ μ l and starting ART within 30 days of TB treatment).

Design: A randomized double-blind placebo-controlled trial to evaluate the incidence of paradoxical TB-IRIS over the first 12 weeks of ART in participants who receive a 4 week course of prednisone versus participants who receive a 4 week course of placebo.

Primary efficacy endpoint:

The development of paradoxical TB-IRIS within 12 weeks of starting ART (defined using the International Network for the Study of HIV-associated IRIS (INSHI) consensus case definition).

Secondary efficacy endpoints:

- 1) Time to IRIS event
- 2) Severity of IRIS events (defined by the following: need for hospitalisation for IRIS, C-reactive protein, and neurological involvement)
- 3) Duration of TB-IRIS event (from onset of symptoms/signs to resolution of TB-IRIS symptoms/signs)
- 4) Mortality attributed to TB and TB-IRIS
- 5) All-cause mortality
- 6) Composite endpoint of death, hospitalization, or hepatotoxicity (using the protocol-specified definition of Grade 3 or 4 increase in ALT or bilirubin).
- 7) Other (non-TB) IRIS events
- 8) Quality of life assessment (measured using PROQOL-HIV, EQ-5D-3L, HIV symptom index and Karnofsky score)
- 9) Adverse events and severe adverse events ascribed to TB treatment, ART or co-trimoxazole. This will include a pre-specified analysis of drug-induced liver injury and drug rash. This assessment will include the number of treatment interruptions for drug adverse events.
- 10) Discontinuation of either ART or TB treatment for > 5 days due to adverse events
- 11) Number of hospitalizations and total days hospitalized

Safety and tolerability endpoints:

- 1) Corticosteroid-associated adverse events, classified by severity and relation to study drug. These will include hypertension, hyperglycaemia, hypomania/mania, depression, acne, epigastric pain, upper gastro-intestinal bleeding, Cushingoid features, new oedema and

avascular bone necrosis.

2) Laboratory safety data: glucose, full blood count and electrolytes

3) Other infections (AIDS-related, bacterial, fungal and viral) and malignancies (Kaposi's sarcoma)

4) All grade 1, 2, 3 and 4 adverse events (clinical and laboratory using the ACTG grading system)

Sample size: 240 participants will be enrolled over 13 months. Each participant will be followed for 12 weeks.

Population: HIV-infected, ART-naïve adult (≥ 18 years) patients diagnosed with active tuberculosis who have a CD4 < 100 cells/ μ L and who start ART within 30 days of starting TB treatment. Other inclusion criteria include: diagnosis of TB (smear, culture, Xpert MTB/RIF test, histology or strong clinical and radiological evidence of TB with symptomatic response to TB treatment), eligible for and consent to starting ART and written informed consent for trial. Exclusion criteria include: Kaposi's sarcoma, pregnancy, TB meningitis or tuberculoma at TB diagnosis (because these patients receive corticosteroids), known rifampicin-resistant TB, being on corticosteroids for another indication within the past 7 days, on other immunosuppressive medication within the past 7 days and uncontrolled diabetes mellitus.

TB treatment and ART: TB treatment will be prescribed and monitored by the clinical staff in the local HIV-TB clinic. TB treatment will be given according to South African Department of Health guidelines. This involves rifampicin (R), isoniazid (H), ethambutol (E) and pyrazinamide (Z) for 2 months followed by RH for 4 months. ART will be prescribed by the clinical staff at the HIV-TB clinic according to South African Department of Health guidelines. Standard first line ART in TB patients is tenofovir, emtricitabine (or lamivudine) and efavirenz. Co-trimoxazole prophylaxis will be prescribed to all patients unless a contra-indication exists.

Intervention: Oral prednisone 40mg daily for 14 doses started on the first day that ART is taken, followed by 20mg daily for 14 doses (or identical placebo). A total of 28 days of study medication will thus be prescribed.

Follow-up: Patients will be screened once established on TB treatment, but before starting ART. If the patient is eligible, written informed consent will be taken. There will be six planned study visits that will be in relation to the start of ART: week 0 (the day ART is initiated), week 1, week 2, week 4, week 8 and week 12. Patients will be seen at unscheduled visits if clinical deterioration occurs. If paradoxical TB-IRIS is diagnosed this will be treated with open label prednisone at clinician discretion if symptoms are moderate or severe. If patients experience clinical complications (eg. TB-IRIS) follow-up will be prolonged beyond week 12 in order to stabilize their condition before referral back to the general TB-HIV clinical service for ongoing management.

Data monitoring: The trial will be monitored by an independent Data and Safety Monitoring Board (DSMB) comprising 3 independent researchers and an independent statistician. After an initial meeting for agreeing on their Charter, the DSMB will meet twice (after 80 and 160

participants have completed follow-up) to review data quality and data with respect to safety and trial endpoints. If there is evidence of harm related to study medication or trial conduct the DSMB may advise the sponsor that trial enrollment should be stopped.

Clinical trial site: Khayelitsha Site B HIV-TB clinic (Ubuntu clinic)

CONTENTS

1. Key roles
2. Executive summary
3. Introduction
4. Study objectives and design
5. Selection and enrollment of participants
6. Study endpoints
7. Study medication
8. Antiretroviral therapy
9. TB treatment

2. EXECUTIVE SUMMARY

Preventing tuberculosis-associated immune reconstitution inflammatory syndrome in high-risk patients: a randomised placebo-controlled trial of prednisone

Tuberculosis (TB) is the most common opportunistic infection amongst HIV-infected patients starting antiretroviral therapy (ART) in developing countries and thus the most frequent form of immune reconstitution inflammatory syndrome (IRIS). Paradoxical TB-IRIS occurs in 8- 43% of patients starting ART while on TB treatment and results in morbidity, hospitalisation, consumes health care resources and TB-IRIS may be fatal. We have previously demonstrated in a clinical trial that prednisone reduces morbidity when used for treatment of paradoxical TB-IRIS. This trial is a double-blind placebo-controlled trial of prophylactic prednisone (40mg/day for 2 weeks followed by 20mg/day for 2 weeks, started on the same day as ART) in patients with TB who are identified as being at high risk for paradoxical TB-IRIS (starting ART within 30 days of initiating TB treatment and $CD4 \leq 100/\mu L$). The trial will enroll 240 participants, randomised 1:1 (prednisone:placebo). The primary endpoint is development of paradoxical TB-IRIS, defined using international consensus case definitions. Secondary endpoints include time to IRIS event, severity of IRIS, quality of life assessment, mortality and corticosteroids adverse events. The trial is powered to determine a reduction in TB-IRIS events. If results of this trial demonstrate benefit and safety, our intention is to take this intervention forward into a larger phase 3 clinical trial with mortality as the primary endpoint.

3. INTRODUCTION

3.1. Primary study objective

To determine whether a 4-week course of prednisone in patients starting antiretroviral therapy (ART) within 30 days of starting treatment for tuberculosis (TB) and a CD4 count \leq 100/ μ L reduces the incidence of paradoxical TB-IRIS, without an excess of adverse events. The trial is powered to determine a reduction in TB-IRIS events. If the clinical trial proposed here demonstrates benefit and safety, our intention is to take this intervention forward into a larger phase 3 clinical trial with a sufficiently large sample size to determine a mortality reduction.

3.2 Paradoxical TB-IRIS

TB is the commonest opportunistic disease in HIV-infected patients in low- and middle-income countries, and is therefore a common indication for starting ART. A substantial proportion of patients starting ART in sub-Saharan Africa are thus on treatment for active TB (up to 42% [1]), and are therefore at risk of paradoxical TB-associated immune reconstitution inflammatory syndrome (TB-IRIS). When ART is commenced in patients on TB treatment an immunopathological reaction, known as paradoxical TB-IRIS, commonly occurs (in 8-43% of TB patients starting ART [2]) resulting in new or recurrent TB signs and symptoms. TB-IRIS causes considerable morbidity; with 30% requiring hospitalization in a prospective study we conducted [3].

One study from the US reported that 44% of patients who developed TB-IRIS required hospitalization for a median of 7 days (range 3-66) and many patients in this study required therapeutic procedures [4]. In a recent report of TB-IRIS cases that occurred during the SAPIt trial in Durban, South Africa (discussed below) among those patients who started ART within 4 weeks of TB treatment who developed TB-IRIS 42% required hospitalization and among those who started ART 8-12 weeks after TB treatment and developed TB-IRIS 22% required hospitalization [5].

Although the mortality of TB-IRIS is relatively low (estimated at 3.2% in a meta-analysis [6]), our group has shown that mortality is about ten times higher than this in patients with neurological manifestations [7, 8]. Importantly, over two-thirds of patients who develop neurological TB-IRIS do not have clinical features of neurological involvement at initial diagnosis of TB [7]. The diagnosis of TB-IRIS is clinical, and it is important to exclude other opportunistic diseases. In resource-constrained settings this puts a strain on over-burdened health services by utilizing diagnostic tests and empiric treatment of suspected alternative diagnoses. In the majority of cases the onset of TB-IRIS is within the first 4 weeks of ART: in our cohort median onset was 14 days (IQR 7-25) [9]. Therefore prophylactic interventions may only be required for one month.

3.3. Corticosteroids in the treatment of TB

Corticosteroids are known to exert anti-inflammatory effects on most types of immune cells through direct effects on transcription of inflammatory mediators via the Glucocorticoid Responsive Element, indirect genomic effects via interference with other transcriptional factors such as NF- κ B and AP-1, and non-genomic effects on anti-inflammatory proteins [10, 11]. These effects result in increased transcription of a number of anti-inflammatory

mediators and decreased transcription of pro-inflammatory cytokines, chemokines, enzymes, receptors and adhesion molecules [12, 13]. In addition, corticosteroids have been shown to reduce T cell survival by enhancing apoptosis [12]. Corticosteroids have been used as adjunctive treatment in TB for several decades [14]. Because the host immune response plays an important part in the pathology caused by TB, corticosteroids have been used in all forms of TB with the intention of improving outcomes and reducing complications such as pericardial constriction, hydrocephalus, focal neurological deficits, pleural adhesions and intestinal strictures. However, evidence of benefit from controlled clinical trials exists only for TB meningitis and pericardial TB as well as paradoxical TB-IRIS [3, 15].

TB Meningitis: Thwaites and colleagues [16] conducted a randomized, double-blind, placebo-controlled trial of dexamethasone for the treatment of TB meningitis in Vietnam amongst patients older than 14 years of age (n=545). The initial dose of intravenous dexamethasone used was 0.4mg/kg/d for patients with Grade 2 and 3 TBM disease and 0.3mg/kg/d in patients with Grade 1 disease. The total duration of dexamethasone (initially intravenous followed by oral) was 8 weeks in those with Grade 2 and 3 disease and 6 weeks in those with Grade 1 disease. At 9 months follow-up, dexamethasone was associated with a reduced risk of death (relative risk = 0.69, 95% CI= 0.52 – 0.92), but no reduction in the proportion of patients with severe disability. Eighteen percent of participants were HIV seropositive and in a pre-specified subgroup analysis of these patients dexamethasone was associated with a non-significant trend towards reduced mortality (relative risk = 0.78, 95%CI = 0.59 -1.04). Significantly fewer severe adverse events occurred in patients who received dexamethasone. In particular, 8 cases of severe hepatitis (one was fatal) occurred in the placebo group and none in the dexamethasone group. This may be an additional benefit of corticosteroids: by reducing drug reactions they prevent treatment interruptions that adversely impact survival. A Cochrane systematic review of corticosteroids as an adjunct to TB treatment in TB meningitis published in 2008 included seven trials and a total of 1140 participants (with 411 deaths). Dexamethasone or prednisolone was the corticosteroid used in all studies. Corticosteroids reduced the risk of death (relative risk = 0.78, 95% CI = 0.67 - 0.91). The survival benefit occurred irrespective of the severity of TB meningitis. Adverse events that occurred across studies included gastro-intestinal bleeding, bacterial and fungal infections and hyperglycaemia, but were mild and treatable [17].

Pericardial TB: A randomized, double blind, placebo-controlled trial of prednisolone (for 11 weeks) for the treatment of TB pericardial effusion was conducted in Transkei, South Africa, in the 1980's prior to the HIV epidemic by Strang and colleagues. Patients in this study were also randomized to open pericardial biopsy and complete drainage of pericardial fluid on admission or percutaneous aspiration when required. Among patients who did not have open drainage on admission, 3% given prednisolone compared with 14% given placebo died of pericarditis (p <0.05) [18]. Patients who received prednisolone required repeat pericardiocentesis less frequently. A Cochrane review [19] of controlled trials evaluating the role of adjuvant corticosteroids for TB pericarditis included 2 trials from the pre-HIV era with a total of 383 participants (the 2 trials included were the study published by Strang and colleagues in 1988 [18] and a prior trial of patients with TB constrictive pericarditis conducted by the same group [20]). There was a non-significant trend towards reduced death in the intervention group (relative risk = 0.65, 95% CI = 0.36–1.16). There was a significant reduction in the combined endpoint of death or disability at 2 years although there

was substantial heterogeneity in the trials. In a small randomised controlled trial of prednisolone for TB pericarditis in HIV-infected patients conducted in Zimbabwe (n=58) [21] there were 10 deaths among those who received placebo compared with 5 deaths among those who received prednisolone. This represented significantly lower mortality in the prednisolone group using the log-rank test to compare Kaplan Meier survival curves [21]. However, when cumulative mortality was compared the difference was not significant (RR=0.50, 95% CI = 0.19 - 1.28) [19]. The Cochrane review concluded that corticosteroids could have clinical benefit, but the trials published to date are too small to demonstrate an effect [19]. In particular, the efficacy and safety of corticosteroids in HIV-infected patients needs to be evaluated in a larger clinical trial.

Corticosteroids are used in other forms of TB. Tuberculomas involving the brain parenchyma or spinal cord may develop despite effective TB treatment resulting in focal neurological deficits or seizures. The host immune response is thought to play an important role in such paradoxical TB reactions. Corticosteroids have been used with anecdotal reports of symptomatic benefit [22]. In miliary and pulmonary TB initiation of TB treatment may be complicated by the development of adult respiratory distress syndrome with acute respiratory failure [23]. Corticosteroids are frequently used in this situation, but efficacy has not been determined in an adequately powered clinical trial. One study of 55 patients with miliary TB showed a non-significant trend towards improved survival with corticosteroids [24]. A review of the literature of corticosteroids used for all forms of TB concluded that corticosteroids do not diminish the efficacy of TB treatment [14].

A recently published meta-analysis of all trials in which corticosteroids were prescribed as adjunctive treatment for TB patients regardless of which organ system was involved, reported that corticosteroids significantly reduced mortality by 17% (relative risk = 0.83, 95% CI=0.74-0.92). This finding was consistent across all organ systems [25].

The above findings mainly apply to HIV-negative patients and there are concerns regarding the use of adjuvant corticosteroids in HIV-infected patients. In a Ugandan trial that evaluated prednisolone in HIV-infected patients with TB pleural effusions, prednisolone was associated with more rapid clinical and radiological improvement, but an excess of Kaposi's sarcoma [26]. A study was conducted in Uganda specifically in HIV-infected patients with pulmonary TB, but prior to ART availability. In this phase 2 trial of short-term prednisolone in HIV-infected TB patients with CD4 count ≥ 200 cells/mm³, prednisolone was associated with more rapid clearance of MTB from sputum, reduced immune activation and resulted in a non-significant increase in CD4 count, but caused a transient increase in HIV viral load and worsened underlying hypertension and caused fluid retention and hyperglycaemia. High dose prednisolone was used in this trial (initially 2.75mg/kg/day for 4 weeks) [27]. Other corticosteroid trials in HIV-infected patients have raised concerns related to reactivation of herpes infections [28]. All patients on our proposed trial will be on ART, and ART is likely to be at least partially protective against certain of these corticosteroid side effects, such as the development of Kaposi's sarcoma.

Corticosteroids have drug-drug interactions with rifampicin, a potent inducer of cytochrome P450 enzymes. Rifampicin increases the clearance of prednisolone by 45% resulting in reduction in the area under the plasma concentration time curve of prednisolone by 66% [29].

We factored this in our decision regarding prednisone dose for this trial.

Corticosteroids in the treatment of TB-IRIS: We have previously conducted a randomised double-blind placebo-controlled trial of prednisone for the treatment of paradoxical TB-IRIS [3]. The trial was conducted at GF Jooste Hospital in Cape Town between 2005 and 2008. 110 patients referred to our hospital and diagnosed with paradoxical TB-IRIS based on a clinical case definition [2] and after diagnostic work-up, were enrolled. Patients with immediately life threatening TB-IRIS (mainly neurological involvement) were excluded and received treatment with corticosteroids in the clinical service. Participants received a 4-week course of prednisone or identical placebo (1.5 mg/kg/day for 2 weeks followed by 0.75 mg/kg/day for 2 weeks). Follow-up was for 12 weeks. The primary endpoint was days of hospitalisation and outpatient therapeutic procedures (counted as an additional hospital day) and this was significantly lower in those who received prednisone (median of 0 days vs 3 days ($p=0.04$)). Prednisone also resulted in significantly more rapid improvement in symptoms, MOS-HIV quality of life score, chest radiology score and reduction in C-reactive protein. There was no excess of corticosteroid metabolic side effects or severe infections in the prednisone arm. There were more mild infections (oral candida and uncomplicated herpes simplex) among those who received prednisone [3].

We have subsequently demonstrated in samples taken from participants on this trial that prednisone, but not placebo, resulted in significant decreases, after correcting for multiple comparisons, in the serum concentrations of IL-6, IL-10, IL-12p40, TNF- α , IFN- γ and IP-10 suggesting that the beneficial effect of corticosteroids in TB-IRIS is mediated, at least in part, through the attenuation of pro-inflammatory cytokine responses [30]. We have previously demonstrated that these same cytokines are differentially increased in the serum of HIV-TB patients who develop TB-IRIS compared to control subjects who start ART and do not [31]. We, therefore, hypothesise that prednisone given from the start of ART may prevent the development of TB-IRIS or at least attenuate its clinical severity through suppression of pro-inflammatory cytokine responses.

Our group also recently reported from an observational study [32] that patients who were on corticosteroids at the time of starting ART (the indication was mainly TBM) had lower interferon γ (IFN- γ), IP-10, tumor necrosis factor- α (TNF- α), interleukin (IL)-6, IL-8, IL-10, IL-12p40, and IL-18 concentrations prior to ART when compared with HIV-TB patients starting ART who were not on corticosteroids ($p \leq 0.02$). In this same study, fewer patients amongst those receiving corticosteroids developed TB-IRIS (38.1% versus 51.7%), but the difference was not statistically significant ($p = 0.287$). We also noted a trend for patients not on corticosteroids to present with more severe TB-IRIS clinical presentations, compared with patients who were on corticosteroids (10/31, 32% vs 0/8, 0% ($p = 0.082$)). The study was relatively small, non-randomised and very likely confounded by indication for prescribing corticosteroids and thus no firm conclusions can be drawn. However, these results suggest there is an important effect of corticosteroids on the immune response in HIV-TB patients starting ART and provide further rationale for this RCT.

Neither corticosteroids, nor any other medication, are currently prescribed for preventing paradoxical TB-IRIS in the current standard of care making a placebo-controlled trial ethically acceptable because it reflects current standard of care.

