3.4. Corticosteroids for other HIV-related conditions

Corticosteroids are used in the treatment of pneumocystis pneumonia (PCP) in HIV-infected patients. A meta-analysis of six randomised trials of adjuvant corticosteroids in the treatment of PCP showed a survival benefit [33]. A 21-day course of corticosteroids used for PCP treatment does not increase the risk of mortality or common HIV-related opportunistic conditions, apart from oesophageal candidiasis [34].

In the ACTG A5164 trial that compared ART timing strategies in patients with non-TB opportunistic and bacterial infections, receipt of corticosteroids during OI management (mainly for PCP) and the timing of ART were not associated with the development of IRIS [35]. However, no cases of IRIS developed while patients were still receiving corticosteroids [36]. In a report of the immunological profile of participants enrolled in this study, amongst patients who had received corticosteroids IFN- γ , IL-6, IL-8, IL-17 and TNF- α and sTNFrII levels were attenuated at time of IRIS [37]. In addition, patients who received corticosteroids, after controlling for the development of IRIS, had lower levels of TNF, sTNFrII and IL8 at baseline compared to those who did not receive corticosteroids [36]. The investigators concluded: “It ... appears that corticosteroids do suppress the same inflammatory markers that seem to identify patients at higher risk for IRIS, lending some support for their empirical use for treatment and potential prevention of IRIS events” [36].

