11.5. Corticosteroid-associated adverse events

Clinical symptoms and signs that could possibly be attributed to corticosteroids side effects will be documented and recorded as corticosteroid-associated adverse events. This will include: new hypertension (resting BP: systolic > 160 mmHg or diastolic >100mmHg), new poor BP control in known hypertensive (who reports adherence to anti-hypertensive therapy, using same thresholds for systolic and diastolic BP), hyperglycaemia (random glucose > 11.1 mmol/l), new oedema, hypomania/mania (diagnosed by psychiatrist), depression (diagnosed by psychiatrist), Cushingoid features or habitus (in the opinion of the clinical investigator),

acne, gastritis symptoms (epigastric pain), upper gastro-intestinal bleeding or avascular bone necrosis. Avascular necrosis will be investigated if patients present with symptoms of bone pain.

Only features that develop while patients are on the study drug or for the 4 weeks afterwards will be classified as corticosteroid side effects.

Infections will not be recorded under corticosteroid side effects but will be recorded and analysed separately.

12. Laboratory evaluation

All laboratory tests (blood and sputum) will be performed at the National Health Laboratory Services laboratories at Green Point or Groote Schuur Hospital. These laboratories are SANAS (South African National Accreditation System) accredited and experienced in performing investigations for clinical research. Hard copy reports of all results will be forwarded to the clinical trial team as soon as the investigation result is available. These will be signed and dated by the trial team. If there is an abnormality then appropriate action will be taken (eg. recalling patient) and this will be documented on the hard copy result. All abnormal investigation results will be communicated to the TB and ART clinic staff.

13. Clinical Management

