14.1. Sample size calculation

Assuming 35% cumulative incidence of TB-IRIS in the placebo arm and a 50% reduction in TB-IRIS in the corticosteroid arm (ie. to 17.5%) and requiring 80% power to test for the difference in TB-IRIS incidence at a two-sided significance level of 5%, the sample size required would be 110 in each arm. We will aim to recruit 240 patients assuming loss to follow-up of 10%. The estimate of 35% incidence of TB-IRIS in the placebo arm corresponds to the findings of Blanc et al (110/332 (33%) of participants who started ART in the early arm in this trial had TB-IRIS events (32)) and a study we conducted at Brooklyn Chest TB Hospital in Cape Town (42% IRIS incidence [47]) and reflects that these will be patients at high risk for TB-IRIS due to low CD4 counts and short interval between TB treatment and ART start. Lawn and colleagues demonstrated in a retrospective study conducted in Cape Town that low CD4 count and shorter interval between TB treatment and ART initiation were the strongest predictors of TB-IRIS. In their study 70% of patients with a CD4 count < 100/μl who started ART within 30 days of TB treatment developed TB-IRIS [48].

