- Hyperglycaemia (random glucose > 11.1 mmol/l)

- Hypomania/mania
- Depression
- Acne
- Epigastric pain
- Upper gastro- intestinal bleeding
- Cushingoid features
- New oedema
- Avascular bone necrosis

b) Comparison of laboratory safety bloods done at week 2, 4 and 12: sodium, potassium, creatinine, ALT, alkaline phosphatase, total bilirubin, glucose, haemoglobin, white cell count, neutrophil count, total lymphocyte count and platelets. Comparison of medians will be performed at each time point using the Wilcoxon rank sum test. The proportion of participants who develop an ACTG grade 3 or grade 4 abnormality in these blood tests will also be compared using Chi-square test or Fisher exact test (as appropriate).

c) Comparison of week 12 CD4 count and HIV viral load results. Comparison of medians will be performed using the Wilcoxon rank sum test. Proportion of participants with less than $2 \log_{10}$ drop in HIV viral load from screening to week 12 will be compared using the Chi-square test or Fisher exact test (as appropriate). Where screening viral load was too low to ascertain a $2 \log_{10}$ drop then an undetectable viral load at week 12 will be regarded as successful outcome.

d) Comparison of the proportion of participants who are diagnosed with other infections (AIDS-related, bacterial, fungal and viral) and malignancies (Kaposi's sarcoma) will be compared using Chi-square test or Fisher exact test (as appropriate). These will also be presented with individual listing. The proportion with severe infections (classified as any AIDS-defining (WHO stage 4) infection or invasive bacterial infection) will be compared in a separate analysis.

e) The proportion of participants with any clinical ACTG grade 1, 2, 3 and 4 adverse events (AEs) will be compared using Chi-square test or Fisher exact test (as appropriate). A similar comparison will be made for serious adverse events (SAEs) and adverse drug reactions (ADRs) attributed as definite, probably or possibly due to medication (the relationship between ADRs and medication has been determined by the study doctors and categorized as definitely not, unlikely, possibly, probably or definitely related to any medication).

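### SAP section 5(d) names no between-arm comparison for mild candida and herpes infections, the infections in which the investigators' own earlier trial saw an excess on prednisone

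*Supplement*

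**What the plan says.** The background in protocol v1.4 points to particular infections.

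- Section 3.3, on the earlier randomised trial of prednisone for treating TB-IRIS: "There were more mild infections (oral candida and uncomplicated herpes simplex) among those who received prednisone". The same paragraph reports no excess of severe infections.
- Section 3.3, on steroids in HIV more generally: "Other corticosteroid trials in HIV-infected patients have raised concerns related to reactivation of herpes infections".
- Section 3.4, on a 21-day course for pneumocystis pneumonia: no added risk of death or of "common HIV-related opportunistic conditions, apart from oesophageal candidiasis".

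On analysis, section 11.5 says: "Infections will not be recorded under corticosteroid side effects but will be recorded and analysed separately". The list in SAP 5(a) accordingly contains no infection, although each of its items, acne included, is compared between arms individually.

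Infections are handled in SAP 5(d). It compares the proportion diagnosed with other infections, with a bracket naming AIDS-related, bacterial, fungal and viral types. It adds an individual listing, and then: "The proportion with severe infections (classified as any AIDS-defining (WHO stage 4) infection or invasive bacterial infection) will be compared in a separate analysis".

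SAP 5(e) compares any clinical adverse event by grade. The closing text of SAP section 5 has adverse events reported by MedDRA preferred term and body system as counts of patients, and runs every safety analysis over 12 weeks and over the first 4 weeks.

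**The concern.** The fourth objective in section 4.1 is safety, and section 3.8 undertakes to analyse infectious as well as metabolic side effects as pre-defined endpoints. The metabolic and clinical effects get item-by-item comparisons. Infections get a broad category and a severe category.

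The severe category is where the earlier trial saw no excess. The mild candida and herpes infections, where it did see one, enter a formal comparison only inside the broad category, alongside every other infection that occurs in patients with CD4 counts of 100 or below. An excess confined to them is diluted there. A non-significant pooled result could then be quoted as reassurance about infection when the test had limited ability to detect the one excess already observed. Section 3.7 expects the trial to inform guidelines if there are no safety concerns, so that reading would matter.

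**Working it through.** **1. The plan's own figure.** The only stated calculation is for the primary endpoint (section 14.1): "Assuming 35% cumulative incidence of TB-IRIS in the placebo arm and a 50% reduction in TB-IRIS in the corticosteroid arm", "requiring 80% power to test for the difference in TB-IRIS incidence at a two-sided significance level of 5" per cent, giving "the sample size required would be 110 in each arm". With p1 = 0.35, p2 = 0.175, d = 0.175 and mean p = 0.2625:

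n = [1.96·√(2·0.2625·0.7375) + 0.8416·√(0.35·0.65 + 0.175·0.825)]² / 0.175² = 98.05, so 99 per arm.

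Continuity-corrected: (98.05/4)·[1 + √(1 + 4/(98.05·0.175))]² = 109.2, so 110 per arm. The stated figure reproduces. It says nothing about infections, for which the documents give neither rates nor a power statement.

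**2. Which comparison covers which infection.**

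| Infection | SAP 5(a) | SAP 5(d) severe | SAP 5(d) other |
|---|---|---|---|
| Oral candida | no | no | yes, read as pooled |
| Uncomplicated herpes simplex | no | no | yes, read as pooled |
| Oesophageal candidiasis | no | yes (WHO stage 4, section 11.2) | yes |
| Chronic or visceral herpes simplex | no | yes (WHO stage 4, section 11.2) | yes |

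The gap is the first two rows.

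**3. Effect of pooling (illustration).** Assumptions: 120 per arm (240 randomised 1:1); two-sided 5% chi-square test, with power by exact enumeration of the two binomials; candida or herpes risk c on placebo and t on prednisone; other infections with risk b, equal in both arms and independent.

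Pooled risk: 1 − (1 − c)(1 − b) on placebo, and 1 − (1 − t)(1 − b) on prednisone.

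The pooled difference is (t − c)(1 − b), so it shrinks as b grows, while the pooled proportions move towards 50%, where the variance is largest. For c = 8%, t = 20% and b = 40%: 1 − 0.92·0.60 = 44.8% and 1 − 0.80·0.60 = 52.0%. A 12-point difference becomes 7.2 points.

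For c = 8% and t = 20%, the combined candida/herpes comparison has **78%** power. Pooled:

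| Background b | Placebo | Prednisone | Power |
|---|---|---|---|
| 5% | 12.6% | 24.0% | 64% |
| 10% | 17.2% | 28.0% | 52% |
| 20% | 26.4% | 36.0% | 36% |
| 30% | 35.6% | 44.0% | 27% |
| 40% | 44.8% | 52.0% | 19% |
| 50% | 54.0% | 60.0% | 15% |

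**4. Other assumed rates.** For 10% vs 25%, power is 88% alone and 50% to 22% pooled at backgrounds of 20% to 50%. For an exact doubling, a dedicated comparison is itself weak: about 48% power for 8% vs 16%, 59% for 10% vs 20%, and 32% for 5% vs 10%.

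**5. One comparison or two.** The 78% belongs to candida and herpes combined. If the 8% vs 20% contrast splits evenly into about 4% vs 10% for each, separate tests have about 46% power each. This favours one combined test, with the separate figures as estimates.

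**The case against.** The strongest reply is that these events would not disappear. SAP 5(d) promises an individual listing, and the MedDRA reporting is by preferred term as counts of patients, so oral candidiasis and herpes simplex should be visible by arm. A reader might infer from the power table that an excess would be missed, or reported as no difference in infections. The documents do not support that: they give no rates, and the listings make complete omission unlikely. What remains is narrower. Neither display carries a named comparison, relative risk or interval.

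A reader might also infer that the SAP tests none of the infections named in the background. That is too strong, since oesophageal candidiasis and chronic herpes fall in the severe-infection comparison.

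The bracket in 5(d) could be read as a list of categories, which would give separate fungal and viral comparisons. The singular proportion, and the separate analysis announced only for severe infection, make pooling the more natural reading, but the text does not settle it.

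Giving severe infections priority is defensible. The excess was mild and came from a trial of treatment, not prevention, at higher doses (section 3.8). Section 3.3 also mentions bacterial and fungal infections generally, in TB meningitis. The undertaking in section 3.8 is met in form by endpoint 3 of section 6.3 and by SAP 5(d); it does not promise organism-specific tests. These points limit the weight of the concern but do not remove it.

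**Conclusion.** The point holds in a limited form. The protocol's own evidence links steroids in HIV to mild candida and herpes infections, and the SAP gives these no named between-arm comparison with an effect estimate. On the natural reading of 5(d), they are tested only within a pooled proportion, which has lower power for them in every scenario tried. Under the assumed 8% vs 20%, power falls from 78% to between 64% and 15%, depending on a background rate that the documents do not state. The direction is secure given equal, independent other infections in the two arms; the size is illustrative.

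It would be wrong to conclude that pooling alone is why a doubling might go undetected. At this sample size a dedicated test detects a doubling at these rates only about 32% to 59% of the time, so the estimate and its interval matter more than the p-value. This is a cheap improvement of minor to moderate weight for a stated safety objective, with no effect on the primary result.

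**What to change.** In SAP 5(d):

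- State that the comparison of other infections is pooled across types.
- Add one pre-specified combined comparison: any candidiasis or herpes (simplex or zoster), at 4 and 12 weeks, with relative risk and 95% CI.
- Report by-arm counts, with relative risk and 95% CI, for candidiasis and for herpes separately, as descriptive rows.
- Keep the pooled and severe-infection tests as they are.

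The cost is SAP wording, one more safety test at the unadjusted 5% level, and two descriptive rows. No new data are needed: section 18.1 records all grade 1 to 4 events, the adverse event CRF in section 16.3 covers opportunistic infections, and both time windows are already set in SAP section 5. The change should be made before unblinding.
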